2. INTRODUCTION

This statistical analysis plan encompasses pre-determined analyses corresponding to the study objectives delineated in the protocol. This Phase 1 pilot, open-label, single-center trial is designed to evaluate the kinetics of *S. hominis* A9 survival on the skin of adults with moderate-to-severe atopic dermatitis on the ventral arms, regardless of *S. aureus* colonization status. The statistical analysis plan (SAP) offers comprehensive information to facilitate the execution of statistical analysis (interim analysis and final analysis) and reporting of the study data for use in the final Clinical Study Report (CSR). This SAP describes the populations that will be analyzed; the participant characteristic parameters, the efficacy parameters, and the safety parameters that will be evaluated; and details of the specific statistical methods that will be used. If additional analyses are required to supplement the planned analyses described in this SAP, they may be completed and will be identified in the CSR. Table, figure, and listing specifications are provided in separate documents.

3. GENERAL ANALYSIS AND REPORTING CONVENTIONS

The following analyses and reporting conventions will be used:

- Categorical variables will be summarized using counts (n) and percentages (%) and will be presented in the form “n (%).” Percentages will be rounded to one decimal place.
- Numeric variables will be summarized using n, mean, standard deviation (SD), median, minimum (min), maximum (max). For data that follow a lognormal distribution (i.e., CoNS CFU), geometric mean and geometric SD will be reported instead of mean and SD.
 - The min/max will be reported at the same level of significance as original data.
 - The mean and median will be reported at one more significant digit than the precision of the data, and SD will be reported at two more significant digits than the precision of the data.
 - The median will be reported as the average of the two middle numbers if the dataset contains an even number of observations.
- Test statistics including t and z test statistics will be reported to two decimal places.
- P -values will be reported to three decimal places if greater than or equal to 0.001. If less than 0.001, the value will be reported as “<0.001.” A p -value greater than 0.999 will be reported as “>0.999”.

If departures from these general conventions are present in the specific evaluations section of this SAP, then those conventions will take precedence over these general conventions.

4. ANALYSIS SAMPLES

4.1 Safety Sample

The safety sample, which will be used for all safety analyses, will include all participants who are enrolled and receive any amount of *S. hominis* A9/placebo. For analysis, *S. aureus* CFU results from swabs obtained prior to treatment application during the Treatment Visit (Day 0) will be used to define SA+ vs SA- status of participants.

4.2 Modified Intent-to-Treat (mITT) Sample

The modified intent-to-treat sample will include all participants who are enrolled and receive any amount of *S. hominis* A9/placebo. For analysis, *S. aureus* CFU results from swabs obtained prior to treatment application during the Treatment Visit (Day 0) will be used to define SA+ vs SA- status of participants.

4.3 Per-Protocol (PP) Sample

The per-protocol sample will include all mITT participants who have no major protocol deviations in the category study medications. Specifically, participants who have no major protocol deviations of the following type: (1) administered study product not approved for distribution (i.e., expired, opened, contaminated, etc.) or (2) the wrong treatment dose (dose does not equal 1 mL or 6 (six) pumps total of placebo or treatment spray per arm). For analysis, *S. aureus* CFU results from swabs obtained prior to treatment application during the Treatment Visit (Day 0) will be used to define SA+ vs SA- status of participants.

4.4 Interim Analysis Sample

The interim analysis sample will include all participants who meet the following criteria:

- Positive for *S. aureus* colonization prior to treatment application at the Treatment Visit (Day 0).
- Application of the ShA9 and placebo treatments.

5. STUDY PARTICIPANTS

5.1 Disposition of Participants

The disposition (i.e., Recruited, Consented, Screened, Eligible, Enrolled, Completed, Discontinued) of all participants will be summarized in tables.

The numbers and percentages of participants enrolled, the numbers and percentages of participants who completed the End of Study Phone Visit (Day 31), as well as reasons for early termination from the study will be presented across *S. aureus* positive/*S. aureus* negative status. Moreover, the study will stratify by arm dominance, with the dominant arm being the right arm for right-handed participants, and the left arm for left-handed participants.

For participants who fail inclusion/exclusion criteria, failed criteria will be listed by participant.

5.2 Demographic and Other Baseline Characteristics

Summary descriptive statistics for demographic characteristics will be reported using conventions from section 3.0. Demographic characteristics collected at the Screening Visit (Day -14 to Day -7) that will be summarized include age (years), sex, ethnicity, race and Body Mass Index (BMI).

A listing for vital signs will be reported. Vital signs and growth parameters are collected during all visits except the End of Study Phone Visit (Day 31) and include systolic blood pressure (mmHg), diastolic blood pressure (mmHg), heart rate (bpm), respiratory rate (respirations/min), temperature (F), height (in), weight (lbs), and body surface area (m²).

Summary descriptive statistics for atopic dermatitis will be reported across arm dominance. Atopic dermatitis severity will be assessed during all visits except the End of Study Phone Visit (Day 31). Atopic dermatitis will be summarized by investigator's global assessment (IGA), local eczema area and severity index (EASI) score on ventral arms, scoring atopic dermatitis (SCORAD) score, and local pruritus numerical rating scale (NRS) of ventral arms.

5.3 Medical History

Medical history is collected during the Screening (Day -14 to Day -7), Pre-Treatment (Day -7), and Treatment (Day 0) visits and will be reported in a listing. An abbreviated medical history will be collected during the Pre-Treatment (Day -7) and Treatment (Day 0) visits.

6. STUDY OPERATIONS

6.1 Protocol Deviations

Protocol deviations will be listed with information such as type of deviation, severity of the deviation (major or non-major), date of occurrence, and the reason for the deviation. Protocol deviations will be summarized by type of deviation.

6.2 Treatment Adherence

Treatment adherence is not applicable to this study as this is a single application administered in clinic.

7. ENDPOINT EVALUATION

7.1 Overview of Efficacy Analysis Methods

7.1.1 Handling of Dropouts or Missing Data

All efforts will be made via the querying and monitoring phases to avoid missing data. In general, missing data will not be imputed.

The data will not be imputed for the primary endpoint. For more details, see Section 7.3

7.1.2 Multicenter Studies

Study participants will be recruited from 1 study site, University of California San Diego.

7.1.3 Assessment Time Windows

Allowable visit windows for all scheduled visits are provided in Section 14.2. All data will be included in analyses, regardless of time of assessment.

Unscheduled visits may also occur throughout the study. Data from unscheduled visits will be included in listings but will generally not be included in tabular or graphical summaries. The one exception is if the unscheduled visit occurs during the allowable visit window of a missed visit, any available data from the unscheduled visit will be included in the summary of the missed visit data.

7.2 Reporting of Swab Results

Prior to the application of the ShA9 and placebo treatment, skin swabs will be collected from the lesional and non-lesional sites on the ventral arms and one non-lesional site on the participant's face. After IP administration to each arm, additional swabs will be collected from the arms 15 minutes and 1, 2, 4, and 6 hours after application. Participants will return to the clinic 24 hours after application (24 Hour Visit) and on Days 3, 10, 17, and 24 for the collection of skin swabs from the identified target sites, as needed. However, after completion of the Day 3 Visit, a participant will not be required to complete the remaining follow up clinic visits (Day 10 through Day 24) once their lesional swabs from both arms (right and left) are CoNS negative, defined as below baseline density measured before application of ShA9 + 100 CFU/cm². The collected swabs will be used to assess the following:

1. *S. aureus* (CFU/cm²)
2. Coagulase negative staphylococcal species (CoNS) (CFU/cm²)
3. *S. hominis* A9 (CFU/cm²)
4. Combined *S. hominis* A9 (CFU/cm²)
5. Combined bacteria DNA (CFU/cm²)
6. Antibiotic-sensitive CoNS

S. aureus will be measured by counting CFUs on the Baird-Parker agar plate. Coagulase negative staphylococcal species (CoNS) will be measured by counting CFUs on the mannitol salt agar with egg yolk plate. CFUs of *S. hominis* A9 will be estimated from total CoNS CFU × % of *S. hominis* A9 positive colonies. Abundance of bacterial DNA from total staphylococcus (G-staph), *S. aureus*, *S. hominis*, and Sh-lantibiotic will be quantified by qPCR. Antibiotic-sensitive CoNS will be estimated from [(CFU without antibiotic containing plate - CFU with antibiotic containing plate)/(CFU without antibiotic containing plate)].

Descriptive statistics and listings by participant of swab results will be presented. Swab results will be plotted to show the trajectory of results over time. Data will be plotted as a spaghetti plot where each

participant's values will be plotted and connected by line segments, forming one line per participant. Plots will also indicate arm dominance per participant.

7.3 Primary Objective

The primary objective for the study is to assess duration of survival of coagulase negative *staphylococcal* species (CoNS) as measured by colony-forming unit (CFU) during a maximum of 24 days after the application of *S. hominis* A9 on the lesional ventral arm skin of Atopic Dermatitis (AD) participants positive for *S. aureus* (AD SA+).

7.3.1 Computation of the Primary Endpoint

Time-to-CoNS elimination is defined as the time from Day 0 to the first occurrence of a value below baseline density measured before application of ShA9 + 100 CFU/cm². The time to event for participants who did not reach CoNS CFU below baseline density measured before application of ShA9 + 100 CFU/cm² during the study will be right-censored.

7.3.2 Primary Analysis of the Primary Objective

The primary endpoint for this pilot study is the time needed for CoNS CFU to drop below baseline density measured before application of ShA9 + 100 CFU/cm² (time-to-CoNS elimination) in AD participants positive for *S. aureus* colonization. Time-to-CoNS elimination will be estimated using Kaplan Meier procedure.

Median survival time along with 95% CI will be constructed based on a log-log transformed CI for the survivor function S(t). A graph of the Kaplan-Meier survival curve will be presented, and rates at fixed days will be derived (Therneau, et al., 2000). Furthermore, estimation of the hazard rate and 95% confidence interval will be produced using a parametric survival model.

The following SAS code will be used to execute this plan:

```
PROC LIFETEST data=data method=KM conftype=loglog plots=(survival(atrisk), hazard);
  title 'Kaplan-Meier plot of CONS CFU Below Baseline (Log-Log)';
  TIME TIME*EVENT(0);
run;
```

The primary analysis will be conducted on the modified intent to treat sample and repeated on the per-protocol sample if it differs from the modified intent to treat sample.

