13.4.2 Primary Analysis of Primary Endpoint

The primary endpoint for this pilot study is the time needed for CoNS CFU to drop below baseline density measured before application of ShA9 + 100 CFU/cm² (time-to-CoNS elimination) in AD participants positive for *S. aureus* colonization. Time-to-CoNS elimination is defined as the time from Day 0 to the first occurrence of a value below baseline density measured before application of ShA9 + 100 CFU/cm². The time to event for participants who did not reach CoNS CFU below baseline density measured before application of ShA9 + 100 CFU/cm² during the study will be right-censored.

Time-to-CoNS elimination distribution (i.e. overall survival) will be estimated using Kaplan Meier techniques. Median survival time along with 95% CI will be constructed based on a log-log transformed CI for the survivor function S(t). A graph of the Kaplan-Meier survival curve will be presented, and rates at fixed days will be derived (Therneau, et al., 2000). Furthermore, estimation of the hazard rate and 95% confidence interval will be produced using a parametric survival model.

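### The primary analysis takes the first swab below threshold as the exact elimination time although later swabs are about 7 days apart, so the median and its lower confidence limit sit at the late end of the swab gap, and the likelihood for the hazard rate is not stated

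*SAP*

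**What the plan says.** SAP 7.3.1 sets the event time: "Time-to-CoNS elimination is defined as the time from Day 0 to the first occurrence of a value below baseline density" plus 100 CFU/cm². Anyone who never gets there is right-censored. SAP 7.3.2 states "Time-to-CoNS elimination will be estimated using Kaplan Meier procedure", passes one time and one event flag per participant to PROC LIFETEST ("TIME TIME*EVENT(0") and adds "Median survival time along with 95% CI will be constructed based on a log-log transformed CI". It then says that "estimation of the hazard rate and 95% confidence interval will be produced using a parametric survival model", without naming a distribution or a likelihood and without code. The exponential appears only in the sample-size text (SAP 11, Protocol 13.7).

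Protocol 13.4.2 plans the same ("will be estimated using Kaplan Meier techniques"). SAP 7.4.2 repeats the approach for non-lesional skin and SAP 10.2 for the interim analysis.

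Post-application swabs are taken at 15 minutes and 1, 2, 4 and 6 hours, and after that (SAP 7.2) "Participants will return to the clinic 24 hours after application (24 Hour Visit) and on Days 3, 10, 17, and 24". Visit windows are ±1 day for Days 3 and 10 and ±2 days for Days 17 and 24 (Protocol Appendix B). SAP 7.1.3 adds "All data will be included in analyses, regardless of time of assessment", which settles which data are used but not how the gap between swabs is treated. Neither document mentions interval censoring.

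**The concern.** A participant above threshold on Day 3 and below it on Day 10 crossed at some unknown time in those seven days. The plan records Day 10. Kaplan-Meier then gives a correct proportion at each visit day, but every drop in the curve sits at the later end of its gap, and so do the median and the lower limit of its interval. A parametric hazard fitted to the same times would count too many days at risk and come out too low.

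There is no formal test, and Protocol 13.6 names estimation of this time as the main goal. Protocol 1.3 wants the rate of elimination to inform dosing frequency, and SAP 10.2 wants it for the design of later trials. The median, the hazard and their intervals are therefore the result. The supportive log-logistic regression (SAP 7.3.3) models CFU against time and corrects neither.

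**Working it through.** **Inputs.** From SAP 11: 13 participants, 9 events, hazard 0.15, 30% censoring, and 0.09 from the earlier trial. Swab times are from SAP 7.2. Assumed: exponential crossing times and rates per day. The unit is not stated, but per day fits the earlier trial: 35 − 9 = 26 events, 26/0.09 = 289 person-days, or 8.3 days each within an 11-day follow-up.

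**The plan's own figure.** The exact interval for an exponential rate has width 0.15 × (χ²₀.₉₇₅,₁₈ − χ²₀.₀₂₅,₁₈)/18 = 0.15 × (31.526 − 8.231)/18 = 0.194. This matches SAP 11, and it treats event times as exactly observed.

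**When the interval for the median can reach back to Day 3.** With k of 13 below threshold by a visit and no dropout, S = 1 − k/13 and the log-log lower limit is S^exp(1.96v), where v = √[k/(13(13 − k))]/|ln S|.
- k = 2: S = 0.846, v = 0.708, lower limit 0.512.
- k = 3: S = 0.769, v = 0.579, lower limit 0.442.

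The median's lower limit is therefore at or before a given visit only if at least 3 of 13 are below threshold by then. The relevant visit is the last one before the true median, ln 2/λ.

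| Rate/day | True median (days) | Visit before it | P(below by then) | P(at least 3 of 13) | Simulated coverage, no dropout |
|---|---|---|---|---|---|
| 0.09 | 7.7 | Day 3 | 0.237 | 0.626 | about 63% |
| 0.15 | 4.6 | Day 3 | 0.362 | 0.903 | 90% |
| 0.20 | 3.5 | Day 3 | 0.451 | 0.974 | 95% |
| 0.24 | 2.9 | 24 h | 0.213 | 0.547 | 54% |
| 0.30 | 2.3 | 24 h | 0.259 | 0.694 | 69% |

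At 0.20 the simulated figure is lower than 0.974 because about 2.5% of trials miss on the other side. At 0.09 and 0.15 nearly all misses put the lower limit above the true median. With exactly observed times, coverage would be 94.4% at 0.15 and 94.5% at 0.09, so the shortfall at those rates comes from the swab gaps and not from the small sample.

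**Where the median lands at 0.15.** It is Day 3 or earlier if at least 7 of 13 are below by Day 3 (probability 0.151), and after Day 10 if fewer than 7 are below by Day 10 (0.013). It is Day 10 in the remaining 1 − 0.151 − 0.013 = 0.836. With dropout this is about 0.80, and with visit windows 0.76 to 0.85.

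**Dropout.** At 0.15 only exp(−3.6) = 2.7% would still be above threshold at Day 24, so 30% censoring needs other losses. Random dropout of 0.041/day supplies them. Simulated coverage is then 94 to 95% at 0.15 and about 76% at 0.09. If dropouts are replaced, as Protocol 11.3 permits, it is 88 to 89% at 0.15.

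**Hazard, if fitted to the single swab time.** The large-sample estimate is [1 − S(24)]/[Σ pⱼtⱼ + 24·S(24)], where pⱼ is the probability of first going below at swab time tⱼ. At 0.15 this is 0.973/9.262 = 0.105, or 30% low. With 13 participants the simulated mean is 0.110 (27% low, interval coverage 74%). With 30% censoring it is 0.116 (coverage 84%). An interval-censored exponential fit on the same swabs covers in 94 to 95%.

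**The case against.** The strongest reply is that SAP 7.3.1 defines the time by an observed value. For time to the first negative swab, Kaplan-Meier is consistent, and the planned interval covers that median in 98 to 99.9% of simulated trials. The shortfall exists only against the time of crossing. This is a fair reading of one sentence, but the objective is duration of survival (SAP 7.3) and the stated goal is the time CoNS need to fall below threshold (Protocol 13.6). A reader of a Day 10 median would not take it to mean some time after Day 3.

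Other points stand.
- At the SAP's own planning case, 0.15 with 30% censoring, coverage is essentially nominal unless dropouts are replaced.
- A reader might infer that coverage worsens steadily as the rate falls. It does not. It depends on where the true median lies between visits.
- A reader might take the 63% at 0.09 as this trial's coverage. The 0.09 comes from an earlier trial with repeated applications and may itself be a first-negative-swab rate. On this trial's swab times it would then correspond to about 0.12/day, with coverage near 80%. It is indicative only.
- A reader might infer that the hazard is biased as planned. The SAP does not say that the single time enters the model, so this is a gap in specification with a known consequence if filled the wrong way.
- Protocol 1.4 reports that in the earlier trial lesional live CoNS was close to baseline about four hours after an application. If elimination falls within 24 hours, where six of the ten post-application swabs lie, the error in the median is hours.
- An unconfirmed low count from swab noise could date elimination too early. That error runs the other way and is not quantified here.

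**Conclusion.** The concern holds, with medium confidence. Treating the first swab below threshold as the exact time places the median and its lower limit at the late end of the gap. At 0.15/day the plan would report Day 10 in about 80% of trials against a true 4.6 days. Coverage of the planned interval ranges from about 54% to 95% over the tabulated rates without dropout, and is about 95% at 0.15 with 30% censoring. The hazard would average about 0.11 for a true 0.15 only if fitted to the single time.

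All figures rest on exponential times, rates per day and 13 participants. Weibull times with the same 4.6-day median give Day 10 in 70% (shape 0.7) to 93% (shape 1.5) of trials, with coverage of 93% and 80%. The documents do not support calling the whole Kaplan-Meier analysis invalid, because survival at the visit days is correct. The change should be made, since it is cheap and bears on the trial's main result.

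**What to change.** In SAP 7.3.2, 7.4.2 and 10.2:

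1. Code each participant as an interval from the last swab at or above threshold before the first swab below it, up to that first swab below, using actual times from application. The lower limit is 0 if the first post-application swab is already below. The interval is open-ended after the last swab if none is below. The words 'before the first swab below' matter, because a later rebound would otherwise give an inverted interval.
2. Report the Turnbull curve (for example PROC ICLIFETEST) and give the median as an interval, such as between Day 3 and Day 10. If the log-log interval is kept with its lower limit moved back one swab, label it conservative (about 99% coverage).
3. Fit the hazard as an interval-censored exponential (for example PROC LIFEREG with lower and upper limits) with a profile-likelihood or log-scale Wald 95% interval, and an interval-censored Weibull as a check. Label any model-based median as model-dependent: under the two Weibull cases above, the exponential median is typically 6.0 and 3.6 days.
4. Keep the Kaplan-Meier plot and the visit-day rates, labelled as time to first negative swab.

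The cost is SAP wording and a few lines of code, with no new swabs or participants. At 0.15/day the mean width of the profile-likelihood hazard interval is about 0.19 without dropout or with replacement, and about 0.22 with 30% unreplaced dropout. Single-time coding gives 0.12 to 0.15, and the plan aims for 0.20. The interval-censored estimate averages 0.163 to 0.166 for a true 0.15, close to the 0.162 that exact timing gives at this sample size. The change does not deal with an unconfirmed first negative caused by swab noise.

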7.3.3 Supportive Analyses of the Primary Endpoint

We propose fitting a nonlinear time-response regression to our data set, which represents the relationship between the concentration of CoNS (Colony Forming Units per cm²) and time. The analysis will be conducted in R, leveraging the package drc known for its robust functionality in the

area of dose-response analysis. Specifically, we will model our data using either a two-parameter or a three-parameter log-logistic regression model.

The following R code will be used to execute this plan:

```
# Load the necessary package
library(drc)

# Fit a two-parameter log-logistic model
model_2par <- drm(CoNS_CFU_per_cm2 ~ time, data = data, fct = LL.2())

# Fit a three-parameter log-logistic model
model_3par <- drm(CoNS_CFU_per_cm2 ~ time, data = data, fct = LL.3())

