mouse skin, are more susceptible to killing by the human AMPs, such as cathelicidin and β -defensins -2 and -3 present on inflamed skin of patients with AD, and ShA9 increases survival upon deletion of its lantibiotics. To further test this hypothesis on human skin in the clinical setting, we measured abundance of ShA9 on the skin of participants from the Phase 1 trial under Protocol ADRN-08. We measured abundance of ShA9 on inflamed and non-inflamed skin. ShA9 abundance was measured by multiple approaches, including direct counting of total CoNS CFUs of live bacteria grown on selective agar plates, abundance of ShA9 DNA by qPCR, and measurement of mRNA by RT-qPCR for candidate ShA9 gene expression. Total CoNS CFUs were used as a surrogate measurement of live ShA9 CFU, since ShA9 is not specifically measurable by colony counting methods. However, since ShA9 is a type of CoNS, and the abundance of ShA9 applied greatly exceeded other CoNS recoverable from AD skin, this estimation was helpful to define live compared to dead bacteria. Furthermore, measurements by qPCR of ShA9 DNA and mRNA provide a more specific method to validate this assumption. On Day 0, an initial swab was collected one hour after application of ShA9 or vehicle. Both lesional and non-lesional skin showed a 3- to 4-log increase in live CoNS on the skin one hour after the first application of ShA9 but no change after application of the vehicle alone (Figure 1.4a). However, a difference in CoNS survival was observed between lesional and non-lesional sites at Days 4 and 7. At these time points, skin swabs were collected approximately four hours after the morning application. Swabs from lesional skin collected at these later times on Days 4 and 7 showed that live CoNS had decreased to a level similar to baseline, and no significant difference was detected in comparison to that from vehicle-treated subjects. This suggested the longer period between the morning application of ShA9 and the skin sampling resulted in a decrease in the live ShA9 recoverable by swab from lesional skin. In contrast, CoNS recovered from non-lesional skin was greater on both Day 4 and Day 7 on participants treated with ShA9 compared to vehicle (Figure 1.4a). These data support our preclinical observations that CoNS-AM+ bacteria survive less well in an inflamed skin environment that will have expression of human AMPs.

Figure 1.4a. CoNS-AM+ persist on non-lesional skin but not on inflamed skin of AD adult participants.

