6.1.1.2. Dosage, Preparation, and Administration

6.1.1.2.1. Dosage - Targeted Density of Transplanted CoNS

There is considerable variability in the abundance of CoNS bacteria on human skin. A recent unpublished study by the UCSD laboratory has found CoNS bacteria with antimicrobial activity can be detected at a range of abundance between 1 x 10² CFU/cm² and 1 x 10⁷ CFU/cm². Therefore, the application of CoNS to a final density between 1 x 10² CFU/cm² and 1 x 10⁷ CFU/cm² is the target goal that will be within the density typically observed on healthy human skin and can be considered safe. This target density for topically applied CoNS bacteria has also been found safe and effective at

inhibiting *S. aureus* in prior studies of both autologous microbiome transplant (Nakatsuji, et al., 2017) and after topical application of *S. hominis* A9 (Nakatsuji, et al., 2021).

Using the body surface area calculations of Mosteller (Mosteller, 1987), we estimate that the smallest potential participant of 4'10" and 85 pounds has a BSA of 1.26 m². The largest participant of 6'3" and 210 pounds has a BSA of 2.25 m². Using the Rule of Nines, each arm is estimated as 9% of the total BSA. Therefore, the ventral surface would be 4.5% of the total BSA. Since one hand is 1% of BSA, the ventral surface of one arm not including the hand would be 3.5% of BSA. Thus, the smallest participant has an area on their ventral arm of 441 cm², and the largest participant 787 cm².

The investigational product will be formulated at a final concentration of bacteria that ranges from 1×10^8 CFU of bacteria/mL to 4×10^9 CFU of bacteria/mL, and a total volume of approximately 1 mL of product will be applied to each participant's arm once. To dispense approximately 1 mL, 6 pumps will be applied per dose (160 μ L/pump). The acceptable dosage range will be between 2×10^3 CFU/cm² and 1×10^7 CFU/cm² to account for variability in participant surface area, bacteria survival, and loss of product during application. The calculated concentration for the arms will be 1.27×10^5 CFU/cm² and 9.07×10^6 CFU/cm² for BSAs of 1.26 m² and 2.25 m², respectively. This range is within the predicted effective and safe concentration of 10^2 CFU/cm² to 10^7 CFU/cm².

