13.4.3 Supportive Analyses of the Primary Endpoint

A nonlinear time-response regression analysis will be fitted between CoNS CFU/cm² and time, using either the two or three-parameter log-logistic model. Each of the models will be fitted to the data, and their fit compared using the Akaike information criteria (AIC), where the model with the lowest AIC will be the primary model for the derivation of the ED50 (or T50, time at which half of the maximum CoNS CFU/cm² is reached) (Ritz, et al., 2015).

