# Select the model with the lowest AIC
best_model <- ifelse(aic_2par < aic_3par, "Two-parameter model", "Three-parameter model")

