# Compute the ED50 (or T50) from the selected model
if (best_model == "Two-parameter model") {
  ED50 <- ED(model_2par, 50)
} else {
  ED50 <- ED(model_3par, 50)
}
```

After conducting the model fits, we will evaluate the Akaike Information Criterion (AIC) for each model to compare their fit. The model yielding the lowest AIC will be selected as the primary model. From this primary model, we will determine the ED50 (or T50) - the time at which half of the maximum CoNS CFU/cm² is achieved. This approach follows the methodology outlined by Ritz et al., 2015. Adjustments or additional steps may be needed depending on the specifics of the data set and the research question at hand.

The supportive primary analysis will be conducted on the modified intent to treat sample and repeated on the per-protocol sample if it differs from the modified intent to treat sample.

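### SAP 7.3.3 fits untransformed CoNS CFU/cm² and pools repeated swabs, so a few high swabs can set the supportive T50

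*SAP*

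**What the plan says.** Protocol section 13.4.3 plans a nonlinear regression of CoNS CFU/cm² on time, with a two- or three-parameter log-logistic curve, where "the model with the lowest AIC will be the primary model for the derivation of the ED50". T50 is the time at which half of the maximum density is reached. SAP section 7.3.3 turns this into code: "model_2par <- drm(CoNS_CFU_per_cm2 ~ time, data = data, fct = LL.2" and "model_3par <- drm(CoNS_CFU_per_cm2 ~ time, data = data, fct = LL.3", followed for the three-parameter model by "ED50 <- ED(model_3par, 50". Neither call contains a transformation, weights, or a participant or curve identifier. The section names no interval method for T50. It closes by allowing adjustments if the data need them, without saying which.

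SAP section 3 says: "For data that follow a lognormal distribution (i.e., CoNS CFU), geometric mean and geometric SD will be reported instead of mean and SD". Of the prior trial, Protocol section 1.4 says that lesional and non-lesional skin "showed a 3- to 4-log increase in live CoNS on the skin one hour after the first application of ShA9". A log scale is mentioned only for the exploratory correlation of *S. hominis* A9 (SAP section 7.5.2). SAP section 12 lists no change to the T50 analysis.

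**The concern.** Least squares on the raw scale assumes roughly equal error variance at all densities. For lognormal data the error grows with the mean, so the highest swabs dominate the sum of squares and the rest of the curve counts for little. Each participant can supply up to 10 post-application swabs (15 minutes, 1, 2, 4, 6 and 24 hours, Days 3, 10, 17 and 24), and the call treats these as independent. T50 can then hang on one or two heavily colonised participants, with a standard error that ignores clustering.

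At stake is the only planned curve-based summary that supports the primary endpoint, in a trial meant to inform dosing frequency (Protocol sections 1.3 and 2.1).

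**Working it through.** **Plan's own figures.** The plan gives no figure for T50. Its one precision figure is the interval width of 0.194 for the hazard rate, and it reproduces: 0.15 × (χ²(0.975; 18) − χ²(0.025; 18)) / 18 = 0.1941 with 9 events. It does not enter section 7.3.3. The calculated starting densities in Protocol section 6.1.1.2.1 also reproduce: 1×10⁸/787 = 1.27×10⁵ and 4×10⁹/441 = 9.07×10⁶ CFU/cm². Their ratio is 71; spread log-uniformly, that is a log10 SD of log10(71)/√12 = 0.53 to 0.54.

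**Why high swabs dominate.** The fit minimises Σ(y − f(t))². I take it as ordinary least squares, because the call names no weights or other error type. Two swabs a factor of 10 apart differ by 10² = 100 in squared size. A swab 2 logs below the peak has 10⁻⁴ of the peak's squared size.

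**Main simulation** (assumptions, since the documents give no variance, slope or T50). There were 13 participants with the swab times above. Swabs stopped after the first visit from Day 3 on with density below measured baseline + 100 CFU/cm², taking the placebo arm as negative. Density was native CoNS plus a log-logistic decay, with log-scale noise.
- T50 was 0.17, 0.5 or 2 days, the slope 1 or 2, and native mean 10² or 10³ CFU/cm² (log10 SD 0.7).
- Larger spread: peak log-uniform over the 71-fold range, log10 SD 0.3 for participants' T50 and 0.35 for swab noise.
- Smaller spread: log10 SDs 0.3, 0.15 and 0.2.

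This makes 3 × 2 × 2 × 2 = 24 scenarios, with 200 trials each. The curves were coded directly; the drc package was not run. Ranges are over scenarios:

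| Result | Larger spread | Smaller spread |
|---|---|---|
| Raw T50 off by more than twofold | 35-51% | 2-25% |
| Log fit with baseline floor, same | 3-27% | 0-2% |
| Log fit without floor, same | 4-55% | 0-28% |
| Leaving out one participant moves raw T50 more than twofold | 38-61% | 2-21% |
| Same, log fit | 0-6% | 0% |
| Top 10% of swabs, share of raw sum of squares | 88-93% | 66-77% |
| Coverage of a 95% interval from the default-type SE, raw fit | 71-86% | 90-97% |

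Example (T50 0.5 day, slope 2, 4-log rise, larger spread): the 5th to 95th percentile of T50 is 0.004 to 1.03 days for the raw fit and 0.25 to 0.68 days for the log fit.

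**Is the raw fit aiming at something else?** No. The half-time of the population arithmetic-mean curve was 0.169-0.171, 0.498-0.502 and 1.995-2.011 days, essentially the assumed values. Against that target the raw fit misses in 34-51% (larger) and 2-25% (smaller).

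**Repeats.** Twelve scenarios with native mean 10² (100 trials each) gave raw misses of 29-58% / 2-21%, against 5-20% / 0-5% for the log fit with floor. All 24 scenarios with 60 trials each gave 23-67% / 3-23% against 5-32% / 0-5%. The floor model missed less often in every scenario of both repeats. With 60 trials the simulation error near 50% is √(0.25/60) = 6.5 percentage points, which explains some of the wider range.

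**A different set-up.** This used 13 × 10 = 130 swabs, T50 4 h, slope 1, upper limit 10⁶, no early stopping and no native CoNS. Between- and within-participant log10 SDs were both 0.3, both 0.5 or both 0.7. The 3 highest swabs carried a median 49%, 73% and 89% of the sum of squares. Deleting them moved the raw T50 by a median factor of 1.8, 2.8 and 6.1, against 1.27, 1.32 and 1.48 on the log scale.

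**The case against.** Several objections have force.

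- A reader might infer that the SAP contradicts itself. It does not quite: the lognormal sentence governs descriptive reporting, section 3 lets specific sections depart from it, and T50 is defined as half of the raw maximum. What stands is that the plan's own view of the data makes the coded fit inefficient and its standard error unreliable.
- The closing sentence of section 7.3.3 lets an analyst react to a visibly bad fit, such as a T50 of 0.004 day (about 6 minutes), before the first swab at 15 minutes. It commits to nothing, so it would be used after seeing the data.
- Taking logs alone is not a reliable cure. Without the floor, the log fit did worse than raw in two scenarios of the 60-trial repeat, with fast decay and high native CoNS. The floor is needed. The simulated data share its form, which favours it.
- The 71-fold range is not observed spread. The product concentration range supplies 40-fold (4×10⁹/1×10⁸), and arm area only 1.8-fold (787/441). The Protocol sets its wider acceptable range "to account for variability in participant surface area, bacteria survival, and loss of product during application", which says that variation is expected but not how much.
- A reader might infer that the AIC step can only return the three-parameter model. The documents do not support that. A two-parameter log-logistic with free slope and T50 needs a fixed upper limit, and the SAP states none; what the software then uses is outside the documents. Even with a limit of 1 assumed, one noisy simulated data set had an AIC gap of only 1.6.
- A reader might also infer that the pre-application swab is entered at time 0. Nothing says so; it needs only a clarifying phrase.

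**Conclusion.** The point holds as a minor one, confined to the supportive analysis. The direction is firm: on data this skewed, the coded fit lets a few high swabs set T50, and its model-based standard error ignores clustering within participant. The size is conditional on assumed variances, slopes and T50 values. Over all runs of the main simulation and its repeats, raw misses beyond twofold were 23-67% with larger spread and 2-25% with smaller spread, against 3-32% and 0-5% for the log fit with a baseline floor. If participants are similar, the problem is modest.

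It would be wrong to infer that the trial's main result is at risk. The Kaplan-Meier estimate, the hazard rate and the sample size do not use T50, and nothing else in the plan depends on it.

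**What to change.** Replace the model in SAP section 7.3.3 and record the departure from Protocol section 13.4.3 in SAP section 12. Suggested content:

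- Fit log10 CoNS CFU/cm² by nonlinear least squares to log10(B + P/(1 + (t/T50)^b)), with P, T50 and b common.
- Use post-application lesional swabs from the ShA9 arm of participants SA+ at Day 0. B is the participant's own Day 0 pre-application lesional density on that arm, held fixed; that swab is not a data point.
- Give T50 a 95% interval that resamples or clusters by participant, for example log T50 ± t (participants minus 1 df) × the SE from a participant-level bootstrap.
- State the value used for a zero count, for example half of the lowest countable density.
- State an upper limit on the CFU scale for the two-parameter model, or drop that model and the AIC step.

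An equivalent log-scale model with a baseline floor and participant effects would also do.

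The cost is wording and code; no new data are needed. T50 becomes the time to half of the excess over baseline, a negligible change after a 3- to 4-log rise. The pooled log curve reads 0-27% low with large spread (within about 10% with small spread), and in the main simulation with slope 1 and large spread it still misses twofold in 19-27% of trials. With 13 participants coverage stays approximate: 86-99% (large) or 86-98% (small) for the t-based bootstrap, against 71-94% or 85-95% for the percentile version. Zero counts were not simulated.
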